4.1 By visit interval

There are several tables needed by interval presentation. If the data are collected at each assessment, then the interval will be targeted at each of the visit. If the data are collected by date only on unscheduled CRF, it will be used to separate the intervals. See below table as guidance on how to separate the intervals.

Visit	Visit Window	Interval	
		Term	Days
1 month	Day 30 ± 7 days	Post OP – 1 month	0-37 days
3 month	Day 90 ± 30 days	>1 month – 3 month	38-120 days
6 month	Day 180 ± 30 days	>3 month – 6 month	121-210 days
12 month	Day 365 ± 30 days	>6 month – 12 month	211-395 days
18 month	Day 545 ± 30 days	>12 month – 18 month	396-575 days
24 month	Day 730 ± 30 days	>18 month – 24 month	576 days-end of study/760 days (whichever is earlier)
End of Study (if > 24 month upper window)	NA	>24 months - End of Study	761 days-end of study

5 Statistical Analysis of the Primary Endpoint

There is no formal statistical hypothesis for this observational post-market study. The study will follow eligible patients implanted with the Phasix™ Mesh for hernia repair in order to assess long-term recurrence rates.

The primary endpoint of the study is Hernia Recurrence Rate.

Hernia recurrence will be assessed by physical examination at each study visit through end of study. A recurrent hernia will be defined as any hernia identified or confirmed by the investigator, during any study follow-up visit, in approximately the same position as the hernia repaired in the study procedure. Potential hernias identified via incidental magnetic resonance imaging (MRI) or computed tomography (CT) scan will be evaluated by the operating surgeon for clinical significance and confirmation of hernia recurrence.

The event will be identified if either of the following questions on “HERNIA RECURRENCE” was answered “Yes”:

“Was there any Evidence of Hernia Recurrence in the Same Approximate Location as the Index Procedure Identified by Physical Exam?”

or

“Was there any Evidence of Hernia Recurrence in the Same Approximate Location as the Index Procedure Identified by Any Other Means?”

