Only the first hernia recurrence of each subject will be counted in the calculation of the hernia recurrence rate. The hernia recurrence rate will be reported for the whole follow up period (post-op to end of study) and by visit using the intervals defined in section 4.1. Only the subjects who did not discontinue the study before the visit window start will be included in the denominator. The 95% confidence intervals of the rates will be estimated by the Binomial exact method.

Kaplan-Meier survival analysis will be performed to estimate the event rates at various time-points (1 month, 3 month, 6 months, 12 months, 18 month, 24 month, End of Study (if out of 24 month visit upper window)). The time to first event will be the time from index-procedure to the first occurrence of the first event.

6 Statistical Analysis of the Secondary Endpoint

The following secondary endpoints will be summarized using descriptive statistics. The secondary endpoints are described in Section 2.2.2.

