7.1 Subjects Dispositions

The summary of the number of subjects enrolled (intent to treat (ITT)), treated with Phasix™ Mesh (mITT), completed the study, and discontinued from the study (by reason of discontinuation) will be provided. Screen failures will be summarized for inclusion/exclusion criteria that were not met.

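### SAP 5 keeps subjects who have already recurred in later by-visit denominators although they can no longer count as events, so later interval recurrence rates are understated

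*SAP*

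**What the plan says.** The primary endpoint is the hernia recurrence rate. SAP 5 fixes the numerator: "Only the first hernia recurrence of each subject will be counted in the calculation of the hernia recurrence rate". Besides a rate for the whole follow-up period, the rate is to be given "by visit using the intervals defined in section 4.1". Those intervals do not overlap: days 0-37, 38-120, 121-210, 211-395, 396-575, 576-760, and a last row, "761 days-end of study".

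The denominator rule is "Only the subjects who did not discontinue the study before the visit window start will be included in the denominator". On precision, SAP 5 says "The 95% confidence intervals of the rates will be estimated by the Binomial exact method". It adds a time-to-first-event analysis: "Kaplan-Meier survival analysis will be performed to estimate the event rates at various time-points".

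Three other places bear on the reading:

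- Protocol 6.5 lists reasons for discontinuation. Recurrence is not among them, although the list is open-ended.
- SAP 7.1 tabulates subjects who "completed the study, and discontinued from the study (by reason of discontinuation") as separate groups.
- SAP 4.1 gives the visit window of the last row, labelled "End of Study (if > 24 month upper window"), as NA.

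**The concern.** A subject whose hernia recurs at month 3 has used up the only event that he or she can contribute. If that subject stays in study, SAP 5 still counts him or her in the 6, 12, 18 and 24 month denominators.

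The resulting figure is not the risk of a first recurrence in the interval, because some of those counted are not at risk. It is not a cumulative rate, because earlier events are left out. Nor is it the share of a fixed cohort, because drop-outs are removed. The exact binomial interval treats every subject in the denominator as able to have the event, and some are not.

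The error runs one way, towards lower late recurrence, and grows from row to row as recurrences accumulate. The stated purpose is to assess long-term recurrence, and Protocol 1.1 puts essentially complete resorption of the mesh at 12 to 18 months. Readers will therefore look at the later rows with interest.

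**Working it through.** **Plan's own figure.** There is none to reproduce. SAP 3.2 says that the 30 subjects rest on no statistical consideration, and no recurrence or drop-out rate is assumed.

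**Inputs.** N = 30 (Protocol 5.1, SAP 3.2). Numerator, denominator and exact 95% limits are from SAP 5, and intervals from SAP 4.1. The number of earlier recurrences *r*, the number of new events *x*, and drop-out are assumptions, shown as ranges.

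**Step 1: the factor.** Let *D* be the subjects not discontinued, and *r* those among them who have already recurred. Before the 24-month visit there are no completers, so:

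- SAP 5 rate = *x*/*D*
- At-risk rate = *x*/(*D* − *r*)
- Ratio of SAP 5 rate to at-risk rate = (*D* − *r*)/*D*

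**Step 2: N = 30, no drop-out, *x* = 2 in a late interval.** SAP 5 gives 2/30 = 6.7% (Clopper-Pearson 0.8 to 22.1, width 21.3 points) whatever *r* is.

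| Earlier recurrences *r* | At-risk rate | Exact 95% CI | Factor (30 − *r*)/30 |
|---|---|---|---|
| 0 | 2/30 = 6.7% | 0.8 to 22.1 | 1.00 |
| 3 | 2/27 = 7.4% | 0.9 to 24.3 | 0.90 |
| 6 | 2/24 = 8.3% | 1.0 to 27.0 | 0.80 |
| 9 | 2/21 = 9.5% | 1.2 to 30.4 | 0.70 |
| 14 | 2/16 = 12.5% | 1.6 to 38.3 | 0.53 |

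With *r* = 6 the correct width is 26.0 points. The last line is an outer bound only: 0.46 × 30 = 13.8, where 46% is the highest figure that Protocol 1.1 quotes for large defects.

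**Step 3: no new events.** The rate is 0% under either rule, but the upper limit is 11.6% with 30 in the denominator, against 12.8% with 27 and 14.2% with 24.

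**Step 4: a whole path.** Take first recurrences of 0, 1, 2, 2, 2, 2 over the six intervals to 24 months, without drop-out. Seven subjects have recurred before the last interval, so SAP 5 gives 2/30 = 6.7% and the at-risk rate is 2/23 = 8.7% (1.1 to 28.0). Chained as conditional risks:

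- SAP 5 rates: 1 − (29/30)(28/30)⁴ = 26.6%.
- At-risk rates: 1 − (29/30)(27/29)(25/27)(23/25)(21/23) = 1 − 21/30 = 30.0%, which equals both the crude proportion 9/30 and Kaplan-Meier.

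**Step 5: expected size under a constant hazard.** For days 576 to 730 and an assumed 24-month risk *R*, the share already recurred is 1 − (1 − *R*)^(576/730) and the interval risk is 1 − (1 − *R*)^(154/730).

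- *R* = 10%: share 8.0%, interval risk 2.2%, SAP 5 rate 2.2% × 0.920 = 2.0%.
- *R* = 20%: share 16.1%, interval risk 4.6%, SAP 5 rate 4.6% × 0.839 = 3.9%.

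Simulation with 10 to 30% uniform drop-out, comparing the two denominators on the same data, gives 1.9-2.0% against 2.1-2.2% for *R* = 10%, and 3.7-3.8% against 4.4-4.6% for *R* = 20%. Both columns fall a little below the interval risk because of drop-out inside the interval, which is a separate effect.

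**Step 6: the row from day 761.** Its visit window is NA, so a rule that refers to the start of the visit window has no value there. Because SAP 7.1 separates completed from discontinued, one literal reading keeps completers. If 25 subjects had not discontinued and 1 event occurred, that reading gives 1/25 = 4.0% (0.1 to 20.4). With 15 truly at risk it would be 6.7% (0.2 to 31.9), with 10, 10.0% (0.3 to 44.5), and with 5, 20.0% (0.5 to 71.6).

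**The case against.** The strongest reply is that SAP 5 already contains correct estimates. Kaplan-Meier for time to first event takes recurred subjects out of the risk set, and the whole-follow-up rate counts each subject once. This stands. A reader might infer that the entire primary analysis is biased, and the documents do not support that. It does not rescue the by-visit rates, however. SAP 5 attaches the exact intervals to them, and Protocol 7.3 asks for rates by visit with confidence intervals and names Kaplan-Meier as additional.

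The second reply concerns size, and most of it stands. Recurrence may be infrequent, and some recurred subjects may leave, since the list in Protocol 6.5 is open-ended. Intervals from 30 subjects are wide under either rule, and no hypothesis depends on them. It would be tempting to quote the effect at 46% recurrence, but that figure is for large defects and is not a planning rate. Protocol 5.2.2 also excludes subjects whose fascia cannot be closed or who need a bridged repair. Nor should the SAP 5 rate be set against the true interval risk, because part of that gap is drop-out within the interval.

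Third, a reader might infer that SAP 5 directs completers into the last row's denominator. The text does not go that far: the rule is undefined there, and keeping completers is only one reading.

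Finally, if by-visit rates were meant to be cumulative, keeping recurred subjects would be right. Earlier events would then have to be in the numerator, and SAP 5 does not say so.

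**Conclusion.** The point holds for the by-visit rates and their exact intervals. As written, numerator and denominator do not match once any subject has recurred and stayed in study. The rate is too low by the share of the denominator that has already recurred, and the interval lies too low and is too narrow.

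The effect is nil with no earlier recurrence, modest with a few, and material only if recurrence is common. These sizes rest on assumed recurrence counts and on recurred subjects remaining in follow-up. Confidence is high in the mechanism and its direction, and lower in any particular size. The last row needs a definition rather than a correction. The change is worth making because the rule is explicit, the error always favours lower late recurrence, and the remedy is cheap.

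**What to change.** In SAP 5, replace the denominator sentence with one to this effect: *For each SAP 4.1 interval, the denominator is the number of mITT subjects who, on the first day of that interval, are still on study (neither discontinued nor completed) and have had no hernia recurrence.* Give the days explicitly, for example day 576 for the >18 to 24 month row and day 761 for the last row. This also removes the ambiguity between the start of the visit window (day 700 for month 24) and the start of the interval (day 576), and it does not select subjects on attendance.

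Label the rate as first recurrence in the interval among subjects at risk, and refer readers to the planned Kaplan-Meier estimates for cumulative recurrence.

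The cost is one SAP sentence, one row label and one condition in the denominator program, with no new data. The downside is that late interval rates become slightly higher and their confidence intervals wider.

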6.1 Device related adverse event incidence

Adverse events that are possibly or definitely related to device are considered. A frequency table grouped by Medical Dictionary for Regulatory Activities (MedDRA dictionary version 16.1) terms (system organ class (SOC) and preferred term (PT)) will be presented.

A frequency table for device related AEs for the whole follow up period (post-op to end of study) and by time intervals (post OP – 1 month/ > 1 month – 3 months/ > 3 months – 6 months/ > 6 months – 12 months/ > 12 months – 18 months/ > 18 months – 24 months/ > 24 months (if any)) presenting the number of events and number of subjects with events will be displayed.

6.2 Quality of life assessments (Carolinas Comfort Scale® and SF-12® - 12-item short form health survey)

The CCS is a 23-item questionnaire that measures three scales: sensation of mesh, severity of pain and movement limitations in the following eight domains: laying down, bending over, sitting up, performing activities of daily living, coughing or deep breathing, walking, walking up the stairs and exercising. The CCS is completed by the subjects at baseline and at all post procedure visits. Each scale score (range from 0-5) is the average across the domains, and the total score (range from 0-5) is the average of the three scales scores.

The CCS three scales scores and total score and their absolute changes from baseline will be descriptively tabulated by visit.

Note: At baseline the scale score “sensation of mesh” and the total score will be calculated for subjects with recurrent hernia and used mesh (see pre-operative diagnoses), if enough values are available. In case of sufficient entries for sensation of mesh at baseline, the absolute change from baseline will be calculated for the scale score “sensation of mesh” and the total score in the subset of subjects with recurrent hernia and used mesh.

The SF-12 version 2 is a multipurpose, 12-item health survey that measures seven domains of health: general health, physical functioning, role limitations due to physical health (role-physical), role limitations due to emotional problems (role-emotional), bodily pain, vitality and mental health, social functioning. It yields scale scores for each of these seven health domains, and two summary measures of physical and mental health: the physical component summary (PCS) and mental component summary (MCS). The SF-12 is completed by the subjects at baseline and at all post procedure visits.

The SF-12 domains and summary measures and their absolute change from baseline will be descriptively tabulated by visit, if scores are available.

6.3 Surgical procedure time as measured from incision to closure (skin to skin)

The surgical procedure time (mins) of the index procedure is calculated as time of skin closure complete minus time of first incision. Summary statistics will be presented for surgical procedure time.

6.4 Length of hospital stay post index surgical procedure

The length of hospital stay (days) is calculated as date of hospital discharge (documented at index procedure) minus date of hospital admission (documented at surgery day (day 0)). The length of hospital stay will be descriptively tabulated.

6.5 Number of study-related post-operative surgical procedures and admissions

Study-related post-operative surgical procedures and admissions will be identified by the AE data with study related AE and requires either “Necessitates Medical or Surgical Intervention” or “New Hospital Admission” (or both). Study related AEs include Possibly Related or Definitely Related to the Device or Procedure. The number of study-related post-operative surgical procedures and admissions for each subject will be summarized for the whole follow up period (post-op to end of study) and by time intervals (post OP – 1 month/ > 1 month – 3 months/ > 3 months – 6 months/ > 6 months – 12 months/ > 12 months – 18 months/ > 18 months – 24 months/ > 24 months (if any)).

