### 3.2 Secondary Endpoints:

1. Device related adverse event incidence
2. Quality of life assessments (Carolinas Comfort Scale® and SF-12® - 12-item short form health survey)
3. Surgical procedure time as measured from incision to closure (skin to skin)
4. Length of hospital stay post index surgical procedure
5. Number of study-related post-operative surgical procedures and admissions
6. Number of study-related post-operative visits unrelated to standard of care.
7. Incidence of Seroma.

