### **8.2 Definition of Serious Adverse Events**

An event will be classified as a serious adverse event (SAE) if it meets the definition of serious injury in the Medical Device Reporting Regulation [21 CFR 803.3] as listed below:

- results in, or contributes to, a death or serious injury;
- is life-threatening (i.e., the subject was at risk of death at the time of the event);
- requires in subject hospitalization or prolongation of existing hospitalization;
- results in persistent disability or incapacity (i.e., permanent impairment of a body function or permanent damage to a body structure);
- necessitates medical or surgical intervention to prevent one of the outcomes listed above in this definition (i.e., to preclude permanent impairment of a body function or permanent damage to a body structure)

NOTE: The term serious is not synonymous with severity, which may be used to describe the intensity of an event experienced by the subject.

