### **8.3 Relationship of Adverse Event to Device/Procedure**

Assess each AE for its relationship to the device (Phasix™ Mesh) or surgical procedures as follows:

- Device: This category should be restricted to AEs directly attributable to devices used as part of the study procedure.
- Procedure: This category should be restricted to AEs directly attributable to the study device surgical procedure.

Use the following categories for assigning the certainty of the relatedness:

- Definitely Related: An AE is definitely related if it is obvious, certain or there is little doubt regarding the relationship.
- Possibly Related: An AE is possibly related if it is capable of being related but relatively unlikely.
- Not Related: An AE is not related if it is determined that there is no plausible association.

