## WARNINGS

1. Device manufacture involves exposure to tetracycline hydrochloride and kanamycin sulfate. The safety and product use for patients with hypersensitivities to these antibiotics is unknown. Use of this device in patients with known allergies to tetracycline hydrochloride or kanamycin sulfate should be avoided.
2. The safety and effectiveness of PHASIX™ Mesh in neural tissue and in cardiovascular tissue has not been evaluated or established.
3. The safety and effectiveness of PHASIX™ Mesh in pediatric use has not been evaluated or established.
4. The placement of PHASIX™ Mesh in direct contact with bowel or viscera is not recommended.
5. If an infection develops, treat the infection aggressively. Consideration should be given regarding the removal of the mesh. An unresolved infection may require removal of the device.
6. This device is supplied sterile. Inspect the device and packaging prior to use to be sure they are intact and undamaged.
7. This device is for single use only. Do not resterilize or reuse any portion of the PHASIX™ Mesh.
8. If unused prosthesis has been in contact with instruments or supplies used on a patient or contaminated with body fluids, discard with care to prevent risk of transmission of viral infections.

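### SAP 6.5 selects events for secondary endpoint 5 with a flag that does not separate medical from surgical intervention, and it states no counting unit

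*SAP*

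**What the plan says.** Protocol 3.2 and SAP 2.2.2 both list, as secondary endpoint 5, the "Number of study-related post-operative surgical procedures and admissions".

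SAP 6.5 turns this into a rule: "Study-related post-operative surgical procedures and admissions will be identified by the AE data with study related AE". The event must also carry one or both of two flags. One reads "Necessitates Medical or Surgical Intervention"; the other marks a new hospital admission. Related means possibly or definitely related to the device or the procedure. The number for each subject is then summarised over the whole follow-up and by interval.

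Three other places bear on this:

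- Protocol 8.2 has a serious-event criterion in almost the same words as the first flag: "necessitates medical or surgical intervention to prevent one of the outcomes listed above in this definition".
- SAP 6.1, for device-related events, names both units of reporting; its table description ends "presenting the number of events and number of subjects with events will be displayed". SAP 6.5 has no equivalent.
- SAP 7.8.5 summarises reoperations by subject and by reoperation, but SAP 6.5 does not refer to it.

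On the smaller points, SAP 6.4 takes length of stay as discharge date minus admission date, while SAP 7.5 takes hospital duration after surgery as discharge date minus surgery date. Protocol 6.1.8 captures all current pain medication at baseline, 12 and 24 months. Protocol 6.3.3 and SAP 7.4 limit the 12- and 24-month capture to hernia-associated medication.

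**The concern.** The endpoint names two kinds of event: a surgical procedure and an admission. The selection rule admits a third, medical treatment without admission, and nothing later in SAP 6.5 takes it out again. A reader of the final table would take each count to be an operation or an admission, and some might be neither.

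Such events are plausible in this setting. The instructions for use state that "An unresolved infection may require removal of the device", so removal is a possible outcome of an infection, not a certain one.

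The missing counting unit is a separate gap. Two programmers could follow SAP 6.5 faithfully and produce different tables. At stake is the accuracy of one descriptive secondary table. No hypothesis test, sample size or primary result depends on it.

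**Working it through.** The documents give no event counts, so there is no planned figure to reproduce. The check sets the rule against the endpoint.

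**1. What the rule selects.** For a related adverse event, reading the flag as worded:

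| Management of the event | Selected by SAP 6.5 | Surgical procedure | Admission |
|---|---|---|---|
| Medical only, no new admission | Yes | No | No |
| Medical only, new admission | Yes | No | Yes |
| Surgical, no new admission | Yes | Yes | No |
| Surgical, new admission | Yes | Yes | Yes |
| No intervention, no admission | No | No | No |

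Only the first row is wrong. Admissions have their own flag, so the fault lies in the procedure part.

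**2. Does it depend on what the flag means?** If the flag is broad, the first row covers any event needing treatment. If it is the Protocol 8.2 criterion, it covers only interventions needed to prevent a serious outcome. That criterion still says medical or surgical, so the row shrinks but is not ruled out.

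**3. Counting unit.** Three hypothetical cases, assuming for illustration one count per event:

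- One event treated only medically, no admission: count 1; procedures 0, admissions 0. Too high.
- One event with two operations in one new admission: count 1; procedures 2, admissions 1. Too low for procedures, and the admission is not shown separately.
- Two events dealt with in one operation, no new admission: count 2; procedures 1. Too high.

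The direction of error is therefore not fixed.

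**4. Size.** Planned enrolment is up to 30 (Protocol 5.1 and 7.2, SAP 3.2).

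- Shift in the mean per miscounted event = 1/N. At N = 30 this is 1/30 = 0.033 per subject, and it is larger if fewer enrol.
- Assume, purely for scale, 10 flagged related events of which 0% to 50% were treated only medically without admission. Then 0 to 5 of the 10 do not belong, which is 0/30 = 0 to 5/30 = 0.167 per subject.

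**5. Interval.** SAP 4.1 says "If the data are collected by date only on unscheduled CRF, it will be used to separate the intervals", but not which date applies when an adverse event and its operation fall on different days. Onset on day 30 with surgery on day 40 falls in 0–37 days by onset and in 38–120 days by procedure. SAP 6.1, 6.7, 7.8.2 and 7.8.3 share this silence.

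**6. Length of stay.** (Discharge − admission) − (discharge − surgery) = surgery date − admission date, the number of pre-operative days. This is zero for anyone admitted on day 0. One pre-operative day in one of 30 subjects adds 1/30 = 0.033 day to the mean.

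**7. Pain medication.** Protocol 6.1.8 and 6.3.3 cannot both hold at 12 and 24 months. SAP 7.4 follows 6.3.3, so its baseline column covers all pain medication and its later columns only hernia-associated use.

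**The case against.** The strongest reply is that adverse-event data are only the means of finding events. Protocol 8.3 asks sites to "Assess each AE for its relationship to the device" or procedure, and the documents record relatedness nowhere else, so a study-related count has to start there. This stands, and the AE-based selection should be kept.

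A reader might go further and infer that SAP 6.5 counts adverse events in place of procedures and admissions. The text does not support that. It says procedures and admissions are identified from those data and that their number per subject is summarised; one count per event is an assumption. What can be said is that the unit is not stated.

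A reader might also infer a substantial over-count. The eCRF is not shown. If the flag is the Protocol 8.2 criterion, an ordinary infection treated with drugs may never carry it, and the instructions for use do not show otherwise. The size is therefore open; the inclusion of medical-only events is not, because both readings of the flag allow it. Equally, minor surgery would be missed only under the narrow reading, which the documents do not establish.

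Finally, the adverse-event listing (SAP 7.8.1) and the reoperation summary (SAP 7.8.5) help a reader of at most 30 subjects to spot discrepancies. They do not correct the endpoint table, and SAP 7.8.5 is neither limited to related operations nor a count of admissions.

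**Conclusion.** The point holds as a mismatch between the named endpoint and its selection rule: events treated only medically, without admission, qualify for a table of surgical procedures and admissions. The missing counting unit is a gap in specification whose effect could go either way. The missing interval date is a lesser gap, common to several tables.

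The number of events affected cannot be derived from the documents and may be small. The figure of 0.033 per subject per event assumes full enrolment of 30. The output is descriptive and the primary endpoint is not affected, so this is a worthwhile clarification of low priority.

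The length-of-stay difference is real on paper but has no effect if every subject is admitted on the day of surgery. The pain-medication conflict within the protocol is real, but pain medication is not an endpoint. A reader might infer that an apparent fall in use is built into the analysis; SAP 7.4 states its scope openly and plans a frequency table by visit, not a change from baseline, so the documents support only a labelling problem.

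**What to change.** **SAP 6.5**

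- Keep relatedness as possibly or definitely related to device or procedure, taken from the adverse-event record.
- Exclude interventions that were medical only and involved no new admission.
- Report distinct surgical procedures and distinct admissions separately, each as number of events and number of subjects.
- Use the reoperation records of SAP 7.8.5 where they can be linked to related adverse events. Footnote any remaining difference from SAP 7.8.5, which is not restricted to related operations.
- If the eCRF cannot separate medical from surgical intervention, relabel the output as related adverse events requiring medical or surgical intervention or new admission.

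One sentence in SAP 4.1 naming the date that assigns an event to an interval would serve all the interval tables.

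**SAP 6.4.** Calculate the post-procedure stay as discharge date minus surgery date, as SAP 7.5 already does.

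**Pain medication.** Reconcile Protocol 6.1.8 with 6.3.3, and label the baseline column of the SAP 7.4 table as having a different scope from the later columns.

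**Cost.** SAP wording, minor reprogramming, and one eCRF check: does it separate medical from surgical intervention, link reoperations to adverse events, and hold procedure and admission dates? The relabelling fallback needs no new data. The downside is that SAP 6.5 and 7.8.5 may still differ and need explaining.
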